### 9.3 PHYSICAL EXAMINATION

Physical examinations are performed at screening, baseline, every 12 weeks thereafter and at EOT. In addition, one examination is also performed at the first post drug elimination follow up visit. Physical examinations should be performed for patients who prematurely discontinued the study treatment.

The Tanner scale (also known as the Tanner stages I-V) is a scale of physical development in children, adolescents and adults (Marshall and Tanner, 1969; Marshall and Tanner, 1970). The scale defines physical measurements of development based on external primary and secondary sex characteristics, such as the size of the breasts, genitalia, and development of pubic hair.

Tanner scale is performed either at the study site by the pediatric neurologist or pediatrician or at a designated site arranged by the investigator. Tanner scale is encouraged to be performed at scheduled visits. However, it is acceptable if the assessments are performed shortly after the scheduled visits due to logistical reasons.

The treating neurologist must assess for neurological signs and symptoms suggestive of a peripheral neuropathy (defined as bilateral sensory and/or motor involvement with stocking glove distribution) at each visit involving a physical examination. If the treating neurologist suspects a peripheral neuropathy then electrophysiological nerve conduction studies must be performed. If the overall assessment of the patient is consistent with a diagnosis of peripheral neuropathy or the worsening of a pre-existing peripheral neuropathy, that event will be reported as AE. If a drug-related peripheral neuropathy is suspected treatment should be discontinued ([Section 1.3](#), [Section 1.4](#), [Section 1.5](#)).

#### **9.4 12-LEAD ECG**

A standard 12-lead ECG will be performed at baseline and at EOT and will be evaluated centrally. For ECG, the variables analyzed will be heart rate, PR interval, QRS interval, QT, QTcB (QTc interval calculated by Bazett's method), and QTcF (QTc interval calculated by Fridericia's method).

In the case of an abnormal ECG (ie, QTcB/QTcF  $\geq$ 500 msec) transmitted to the centralized ECG system and manually interpreted by the cardiologist in the centralized ECG facility, a cardiology consultation should be performed, and consideration is should be given to placing the patient under supervision in a specialized setting.

A confirmed prolonged QTc interval (QTcB/QTcF  $\geq$ 500 msec) should be reported in an expedited fashion by the centralized ECG system. An expedited notification of the finding of QTc interval prolongation is communicated to the investigator and to the Sponsor ([Section 1.3](#), [Section 1.4](#), [Section 1.5](#)).

#### **9.5 ULTRA SOUND OF THE PANCREAS**

An ultrasound will be performed for patients with confirmed pancreatic enzymes elevation  $\geq$ 3 x ULN and/or symptoms suggestive of pancreatitis.

The ultrasound examination will be performed according to local standards. A gastroenterologist will review the report and provide clinical conclusion. Abnormal findings should be reported as AEs.

All ultrasounds with abnormal pancreatic findings must be followed by a CT scan with contrast or MRI of the pancreas and report added to the CRF.

## 9.6 CLINICAL LABORATORY PARAMETERS

The Central Laboratory performs clinical laboratory assessments. This includes two-parts: for scheduled study center visits, laboratory samples will be drawn at the site and samples will be shipped to the Central Laboratory to be analyzed; for safety laboratory samples collected locally in between site visits, blood samples are drawn locally but are shipped to the Central Laboratory for analyses. Fasting is not required, but the information on fasting/non fasting conditions will be collected. Local anaesthetic must be offered for blood draws to minimize pain and discomfort. A specific written manual regarding the mechanisms and procedures related to the centralized laboratory process is provided to each investigator (see [Section 1.3](#), [Section 1.4](#), [Section 1.5](#)).

For a regional or national emergency declared by a governmental agency, contingency measures are included in [Section 17.7](#).

### 9.6.1 Routine clinical laboratory parameters

The following routine parameters will be measured at screening, randomization, Weeks 4, 12 and then every 12 weeks and at EOT:

- Hematology and differential panel (hemoglobin, hematocrit, red blood cell count and red blood cell morphology, mean corpuscular volume, white blood cell count, neutrophils, lymphocytes, monocytes, eosinophils, basophils, platelets).
- Coagulation panel (prothrombin time, and activated partial thromboplastin time).
- Complete chemistry panel (glucose, creatinine, blood urea nitrogen (BUN), sodium, potassium, chloride, bicarbonate, magnesium, uric acid, aspartate aminotransferase (AST), alanine aminotransferase (ALT), gamma-glutamyl transpeptidase (GGT), lactate dehydrogenase (LDH), total bilirubin, direct/indirect bilirubin, alkaline phosphatase, calcium, inorganic phosphorus, total protein, albumin, globulin, albumin/globulin ratio, triglycerides, cholesterol and creatine phosphokinase (CPK).
- Pancreatic enzymes (serum amylase and lipase).
- Urinalysis (pH, ketones, protein, glucose, blood, urobilinogen, bilirubin, microscopic sediment, specific gravity).
- For pubescent females serum pregnancy test  $\beta$ - Human chorionic gonadotropin ( $\beta$ -HCG) (NOTE: This test is performed at baseline and every 12 weeks and at EOT or premature treatment discontinuation).

### 9.6.2 Safety clinical laboratory parameters

The following safety laboratory testing will be conducted in between clinical routine lab at Weeks 8, 16, 20, 30 and then every 12 weeks up to the EOT, measuring hematology and differential panel as above

- Liver function tests [ALT, AST, GGT, total bilirubin, and direct/indirect bilirubin].
- Pancreatic enzymes [serum amylase and lipase].

At EOT+2 weeks and EOT+4 weeks:

- Uric acid and inorganic phosphorus will also be performed.

Note: Any abnormal laboratory value will be immediately rechecked for confirmation before making a decision of permanent discontinuation of Investigational Product for the concerned patient.

Threshold values for laboratory parameters of special concern (ie, liver enzymes, pancreatic enzymes and neutrophil counts) are defined for monitoring purposes as AEPMs with expedited reporting when thresholds are met; (ie, Neutrophils < 1000/mm^3, ALT > 3 x ULN and Bilirubin > 2 x ULN for liver function according to see 17.4), and AEPMs (see Section 9.8.1).

### 9.6.3 Additional laboratory parameters

TSH: at baseline, every 24 weeks and EOT.

### 9.6.4 Optional additional extension period for young patients

After the patient has entered the optional additional extension period, laboratory tests will be performed upon investigator discretion based on signs/symptoms of adverse reactions.

## 9.7 IMMUNOGLOBULINS

Serum immunoglobulins concentration (IgG, IgM and IgA) at randomization and every 24 weeks.

In addition if a patient has a vaccination, antibody titers will be assessed before and after vaccination (only inactivated vaccines are allowed)

## 9.8 SAFETY INSTRUCTIONS

### 9.8.1 Pre-defined adverse events and laboratory abnormalities for specific reporting (AEPM)

For the following events, the Investigator should follow the procedures for specific expedited reporting in order to assure Sponsor monitoring and DMC review, even if the criteria for seriousness are not fulfilled. The Investigator is required to completely document the evaluations and treatments and provide them to the Sponsor. For all of these events the “Safety complementary form” has to be completed in the eCRF. For some of the listed events specific CRF pages have to be completed in addition to that.

All the following adverse events must be monitored until symptom resolution or until the condition stabilizes

Instructions for reporting and Follow-Up:

- Confirmed ALT >2 x ULN by a retest done as soon as possible (in 7 days if ALT ≤3 x ULN). See 17.4 for guidance of reporting and Follow-Up (note that only ALT is to be taken into account in the aminotransferase figure).
- Any occurrence of ALT >3 x ULN with total bilirubin value >2 x ULN. See 17.4 for guidance of reporting and Follow-Up.
- Any occurrence of ALT >8 x ULN. This should be reported as SAE with the criteria of medical importance. See 17.4 for guidance of reporting and Follow-Up.
- Depressive disorder that is considered clinically important by the investigator;
- Any occurrence of confirmed (by a retest) neutrophil count of less than 1000 cells/ $\mu$ L. See 17.4 for guidance of reporting and Follow-Up.
- Confirmed serum amylase or lipase >2 x ULN by a retest done as soon as possible (up to 14 days).  
(Amylase or lipase values greater than 2 x ULN and less than 3 x ULN must be repeated within 7 days and weekly thereafter until it is less than 2 x ULN. Amylase or lipase values greater than 3 x ULN must be repeated within 48 hours and every 48 hours until it is less than 3 x ULN and weekly until it is less than 2 x ULN. Study medication must be discontinued if serum amylase or lipase values are greater than 2 x ULN and associated with signs or symptoms consistent with pancreatitis. Study medication must also be discontinued if serum amylase or lipase values are greater than 5 x ULN, confirmed within 48 hours, and without signs or symptoms of acute pancreatitis. In this case, a thorough evaluation for the basis of these elevations must be performed.)
- Abdominal CT or MRI scan with findings with pancreatic abnormalities;
- Pulmonary symptoms such as onset or worsening of cough or dyspnea requiring pulmonary evaluation and consistent with a pulmonary toxicity.
- Peripheral neuropathy confirmed by nerve conduction study.  
All neurological symptoms suggestive of a peripheral neuropathy will be followed up with nerve conduction studies.
- Any sign, symptom, laboratory data suggestive or evocative of renal dysfunction with acute renal failure, as defined by a rapid increase in serum creatinine over 150  $\mu$ mol/L or rapid decrease in creatinine clearance below 50ml/min (See 17.4 for guidance of reporting and Follow-Up).
- Severe skin reaction such as toxic epidermal necrolysis or Stevens Johnson syndrome.
- Sustained increase in blood pressure: SBP  $\geq$ 160 mmHg, DBP  $\geq$ 100 mmHg on at least 2 consecutive visits.
- Other reasons for expedited reporting:
  - Overdose (see Section 9.8.4). An overdose (symptomatic or not) with the IMP is an event suspected by the Investigator or spontaneously notified by the patient and defined as at least twice the intended dose (ie, 2 tablets) on a given calendar day. The circumstances (ie, accidental or intentional) should be clearly specified in the verbatim and symptoms, if any, entered on separate AE form,

- Any pregnancy diagnosed in a female subject or in the female partner of a male subject during treatment with the IMP must be reported to the Sponsor immediately. The treatment should be withdrawn and the accelerated elimination procedure performed. Information related to the pregnancy must be provided to the Sponsor. Information related to the birth of a child of an exposed patient must be provided to the Sponsor. The “Drug exposure via parent” form must be completed.

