- f* If patient is treated with steroids the MRI should be performed after 14 days discontinuation of the steroids. No central reading for MRI is planned in the optional additional extension period.
- g* During the adverse event reporting process, specific questions about pulmonary symptoms and peripheral neuropathy symptoms will be asked. (Patients will be instructed to alert the treating physician of symptoms suggestive of immunodeficiency).
- h* Including systolic and diastolic blood pressure, heart rate, body temperature, weight and height; patient standing in bare or stocking feet. Height and weight is to be documented in the growth charts –Blood pressure (BP) and heart rate to be measured in both the supine and the standing positions (measures taken 3 minutes after supine and 3 minutes after standing). A sphygmomanometer with a blood pressure cuff appropriate to the patient's arm girth is used. Of note, during remote visits, only weight will be collected.
- i* Standard liver function test and hematology tests to be performed every 6 weeks (specific panel to be decided by Investigator). These tests will be performed in local laboratories. Clinical relevant abnormalities should be reported as TEAEs (Refer to [Section 9.10.2.1](#)). Other data will not be entered in eCRF.
- j* Post drug elimination procedure: samples to be collected for verification of plasma teriflunomide concentrations  $\leq 0.02$   $\mu\text{g/mL}$ .

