### 6.3.4 Criteria to reduce reproductive risk

The effect of teriflunomide on human fetal development is not known, and may be potentially harmful based on results from animal studies. Therefore, all patients must be fully informed as to this risk and provide written consent /assent to not become pregnant or father a child during their participation in this study. If during the study, a female patient becomes pregnant or decides to attempt to become pregnant or if a male patient decides to attempt to father a child, then she or he must stop the study medication and undergo the accelerated elimination procedure.

Female patients must not be breast feeding or pregnant (as confirmed by serum pregnancy test) at the time of study entry and must agree to undergo serum pregnancy testing throughout the study at each 12-week clinic visit. In addition, pregnancy test should be conducted in case of an unexpected delay of menstruation.

Definition of “woman not of child bearing potential”:

- Be sterilized (eg, hysterectomy, bilateral oophorectomy, bilateral salpingectomy or bilateral tubal ligation).

A woman of child bearing potential (WOCBP) is any female who has experienced menarche and does not meet the criteria for “woman not of child bearing potential”.

Women of child bearing potential and male subjects must agree that they will take means to reduce reproductive risk by agreeing to use a double method of contraception (ie, an acceptable method in both female and male) until successful plasma elimination has been confirmed (refer to [Section 9.9](#)). Acceptable methods of contraception are defined for this protocol as:

- For male:
  - True abstinence: when this is in line with the preferred and usual lifestyle of the subject (Periodic abstinence [eg, calendar, ovulation, symptothermal, post ovulation methods] and withdrawal are not acceptable methods of contraception),
  - Male sterilization (with the appropriate post vasectomy documentation of the absence of sperm in the ejaculate),
  - Use of condoms throughout the study, in addition to spermicides is recommended.
- For women of child bearing potential:
  - True abstinence: when this is in line with the preferred and usual lifestyle of the subject (periodic abstinence [eg, calendar, ovulation, symptothermal, post ovulation methods] and withdrawal are not acceptable methods of contraception),

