## **9.9 ACCELERATED ELIMINATION PROCESS**

Oral intake of cholestyramine or activated charcoal significantly accelerates the elimination of teriflunomide. The preferred washout medication is cholestyramine. Without using the accelerated elimination procedure, it may take years for teriflunomide plasma concentrations to reach acceptable low levels ( $\leq 0.02$   $\mu\text{g/mL}$ ) due to the long elimination half-life. All patients who complete or discontinue the study drug must undergo one of the accelerated elimination procedures described below. These procedures must be carried out at the study site by the Investigator. For patients who will continue to the commercially available drug, no accelerated elimination procedure is required.

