**Table 2 - Washout medications and dosage**

	Cholestyramine	Activated Charcoal
Washout (11 days)	240mg/kg/day TID	2 x 50 g = 100 g daily

After treatment with either cholestyramine or activated charcoal taken for 11 days, the teriflunomide plasma concentration has to be verified as  $<0.02 \mu\text{g/mL}$  prior to withdrawal from/completion of the study. A post-washout PK sample will be collected immediately following administration of washout medication and at both post-drug elimination follow up visits (EOT+2W and EOT+4W). The PK samples after washout will be labeled separately from the regular pharmacokinetic samples (using labels and tubes provided in the Washout lab kit) and will be analyzed using a more sensitive bioanalytical assay (see [Section 9.11.3](#)). Feed-back on plasma levels above  $0.02 \mu\text{g/mL}$  will be provided only when requested by the Investigator, eg, in case of desired pregnancy. This is applicable for women or men wishing to parent a child, or in specific situations, including planned prescription of fingolimod, natalizumab or mitoxantrone. If the sample collected at EOT+2 weeks has blood plasma levels of teriflunomide  $>0.02 \mu\text{g/mL}$ , the site will be notified at EOT+4 weeks and the cholestyramine/charcoal treatment should be repeated. The level should continue to be followed every two weeks until it is equal or below  $0.02 \mu\text{g/mL}$ .

Both cholestyramine and activated charcoal may influence the absorption of estrogens and progestogens and reduce the effectiveness of oral contraceptives; therefore, the use of alternative contraceptive methods for women is recommended during the accelerated elimination procedure.

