2.1.4.3 Laboratory safety variables

Clinical laboratory data consists of blood analysis, including hematology, clinical chemistry, and urinalysis. Clinical laboratory values after conversion will be analyzed into standard international units and international units will be used in all listings and tables.

Blood samples for routine clinical laboratories will be taken at Screening, randomization, Weeks 4, 12 and then every 12 weeks up to the EOT (Week 96, premature treatment discontinuation visit and the time when patient switches to the open label period after a clinical confirmed relapse or high MRI activity whichever comes first) in the double-blind period, and then at transition, Weeks 4, 12 and then every 12 weeks up to the EOT (Week 192 or premature treatment discontinuation visit whichever comes first) in the open-label period. The laboratory parameters will be classified as follows:

- Hematology
 - **Red blood cells and platelets and coagulation:** hemoglobin, hematocrit, mean corpuscular hemoglobin, red blood cell count, platelet count, prothrombin time, activated partial thromboplastin time
 - **White blood cells:** white blood cell count, neutrophils, lymphocytes, monocytes, basophils, eosinophils
- Clinical chemistry
 - **Metabolism:** glucose, cholesterol, triglycerides, total protein, albumin, globulin, albumin/globulin ratio, creatine phosphokinase(CPK), serum amylase and lipase
 - **Electrolytes:** sodium, potassium, chloride, calcium, inorganic phosphorus, bicarbonate, magnesium
 - **Renal function:** creatinine, creatinine clearance, blood urea nitrogen (BUN), uric acid
 - **Liver function:** alanine aminotransferase(ALT), aspartate aminotransferase(AST), alkaline phosphatase, Gamma Glutamyl Transferase(GGT), lactate dehydrogenase (LDH), total bilirubin, direct/indirect bilirubin
 - **Pregnancy test:** Serum β -human chorionic gonadotropin (β -HCG) for pubescent females (NOTE: This test is performed at screening, randomization and then every 12 weeks and EOT in the double-blind period, and then every 12 weeks and EOT in the open-label period)
- Urinalysis - quantitative analyses: pH, ketones, protein, glucose, blood, urobilinogen, bilirubin, microscopic sediment and specific gravity

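### Pregnancy reporting covers diagnoses made on treatment, but the protocol's own risk window runs to confirmed drug elimination; the pregnancy-testing statements also need reconciling

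*Protocol*

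**What the plan says.** **Reporting.** Protocol section 9.8.1, under the other reasons for expedited reporting: "Any pregnancy diagnosed in a female subject or in the female partner of a male subject during treatment with the IMP must be reported", with immediate notice to the sponsor. The same paragraph also asks for birth information when the parent was an exposed patient, without repeating the limit to treatment.

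**Risk window.** Section 6.3.4 requires double contraception "until successful plasma elimination has been confirmed". Section 9.9 explains why: without the accelerated procedure "it may take years for teriflunomide plasma concentrations to reach acceptable low levels". It also notes that the two washout agents "may influence the absorption of estrogens and progestogens and reduce the effectiveness of oral contraceptives".

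**Testing up to EOT.** Section 6.3.4 says female patients "must agree to undergo serum pregnancy testing throughout the study at each 12-week clinic visit", and adds a test when menstruation is unexpectedly late. On the serum test, section 9.6.1 says "This test is performed at baseline and every 12 weeks and at EOT or premature treatment discontinuation". SAP section 2.1.4.3 agrees for the open-label period: "and then every 12 weeks and EOT in the open-label period".

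**Testing after EOT.** Section 10.1.4 and footnote l of flow chart 1.2 list the laboratory work at EOT+2W and EOT+4W as haematology, liver function, pancreatic enzymes, uric acid and phosphorus. Neither lists a pregnancy test.

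**Optional extension.** Visits are 24 weeks apart (section 10.1.6). Footnote i of flow chart 1.5 reads "Standard liver function test and hematology tests to be performed every 6 weeks (specific panel to be decided by Investigator"), with local laboratories. Section 9.6.4 instead leaves laboratory tests to the investigator's discretion. None of these places lists a pregnancy test.

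**The concern.** The protocol ties reproductive risk to plasma level but ties pregnancy reporting to the date of diagnosis relative to dosing. The two end at different times. A conception late in treatment that is recognised after the last dose, or a conception during washout, is an exposed pregnancy by the protocol's own reasoning, yet no sentence plainly requires it to be reported. The washout period is also when the protocol says oral contraceptives may work less well.

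Section 3.1.2.2 reports embryofetal toxicity in rats and rabbits, and section 6.3.4 calls the human effect unknown and potentially harmful. Few pregnancies are to be expected in a trial of 165 patients aged 10 to 17, so losing even one outcome matters to the safety record. Efficacy inference is not affected.

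**Working it through.** The plan states no figure on this point. The check sets the windows side by side and makes three simple counts.

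**Where each window ends**

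- Contraception (6.3.4): confirmed elimination. Section 9.9 sets the threshold at 0.02 µg/mL and continues sampling every two weeks if the level stays above it.
- Pregnancy reporting (9.8.1): end of treatment with study drug, judged by the date of diagnosis.
- Scheduled pregnancy test (9.6.1; SAP 2.1.4.3): EOT or premature discontinuation. Flow chart 1.2 defines EOT as the first visit after the last intake. On strict wording, even a pregnancy found by the EOT test is diagnosed after treatment has ended.
- Adverse event collection (9.1): through the post-elimination follow-up. Pregnancy is not named, and partners of male patients are not trial patients.
- After-study reporting (9.10.2.3): only a serious or pre-specified event that the investigator considers caused by the study drug.

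The first window is longer than the second and third, and the last two do not clearly fill the difference.

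**Length of the gap.** EOT to EOT+4W is 4 × 7 = 28 days, assuming that the EOT+4W sample is the one that confirms elimination. Scheduled pregnancy tests in that span: 0. After early discontinuation, the 12-weekly follow-up in section 10.3.2 lists none either.

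**Patients with a longer gap.** Section 7.3.1 expects more than 97% of treated patients to reach a low enough level after the recommended procedure. 100% − 97% = 3%, so fewer than 0.03 × 110 = 3.3 of the patients planned for teriflunomide. If all 165 eventually took active drug through the open-label period, the ceiling would be 0.03 × 165 = 4.95. Both counts include boys and girls, and both include patients who never stop without continuing teriflunomide.

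**Extension.** Section 7.1 defines teriflunomide as study drug, so section 9.8.1 covers extension patients until their last dose, and the gap there is in testing only. Flow chart 1.5 runs to extension week 216. At the 12-week interval of section 6.3.4 that would be 216 / 12 = 18 tests, against 0 listed. The 18 is an upper bound: the rationale for amended protocol 3 (section 17.9) expects patients to be at least 14, and treatment ends at 18 or on an earlier switch to commercial product. That gives at most 18 − 14 = 4 years, or 4 × 52 = 208 weeks and 208 / 12 = 17 whole intervals, with fewer for anyone older at entry.

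**The case against.** Several counter-arguments have weight.

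- **Other routes exist.** Section 6.3.4 requires a test on delayed menstruation, with no tie to EOT. Section 9.8.1 asks for birth information for exposed patients. Adverse event collection runs through washout, and a congenital anomaly is a serious event. The causality condition in section 9.10.2.3 applies only after the patient's study has ended, and washout lies before that. This narrows the gap. It does not close it: the menstruation test depends on recognition and does nothing for partners, the birth sentence carries no trigger for reporting the pregnancy itself, and an anomaly is known only at the end.
- **The extension may lie outside the study.** Sections 3.1.2.4, 5.1 and 5.1.1 offer it to patients on completing the study, it has no 12-weekly clinic visits, and section 17.9 describes conditions close to clinical practice, with the Investigator's Brochure and product labels to be taken into account. That reading is reasonable, and what those labels require cannot be seen here. But the protocol does not say that section 6.3.4 ceases to apply.
- **Few patients are affected.** This is correct. Patients moving straight to commercial teriflunomide need neither the elimination procedure nor the post-washout visits (sections 9.9 and 10.1.4), and patients who took only placebo were not exposed.

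A reader might infer more than the documents support:

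- That extension pregnancies go unreported. They do not, because those patients take study drug.
- That exposure without reporting could last for years. Section 9.9 speaks of years only without the procedure, makes the procedure obligatory for patients not continuing the drug, and gives no rate of refusal.
- That about 18 tests per girl are missing. That count is a ceiling and presupposes that section 6.3.4 applies in the extension.

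**Conclusion.** The reporting rule is narrower than the risk window that the protocol itself defines. Applied literally, it omits pregnancies in patients or partners that are first diagnosed between the last dose and confirmed elimination. This concerns only patients who stop and do not continue teriflunomide. The exposed period is about 4 weeks, longer for the fewer than 3% expected not to clear. That size rests on the clearance expectation in section 7.3.1 and on the EOT+4W sample serving as confirmation.

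On testing, the schedule ends at EOT, and the test for delayed menstruation reduces the remaining gap without removing it. In the extension no test is scheduled, which contradicts section 6.3.4 unless the extension is held to be outside the study; the text leaves this open.

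This is a matter of safety-data completeness and internal consistency, with no bearing on sample size, alpha or power. It is still worth correcting: each such pregnancy is informative and the change is small.

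**What to change.** 1. In section 9.8.1, align the pregnancy-reporting window, for patients and partners, with the risk window that section 6.3.4 already defines, so that it also covers pregnancies diagnosed after the last dose and before confirmed elimination.
2. Reconcile the pregnancy-testing statements in sections 6.3.4, 9.6.1, 9.6.4, 10.1.4 and 10.1.6 and in flow charts 1.2 and 1.5. State whether section 6.3.4 applies in the optional extension. Sections 9.6.4 and 10.1.6 also differ on whether extension laboratory tests are routine or discretionary, and should be settled in the same pass. Whether and when pregnancy tests are done is for the medical team.

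The cost is amendment wording, and a few additional reports if pregnancies occur. Any testing cost depends on what the medical team decides; extension laboratory work is local and mostly not entered in the case report form.
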